1. BACKGROUND

In recent years scientific researches showed that the PCO rate of MICS intraocular lenses may be higher than the PCO rates known from conventional intraocular lenses (IOLs). Until now, from our own studies, 5 MICS intraocular lenses showed significantly higher PCO rates.

Since September 2008, the intraocular posterior chamber MICS lens L-313 from OSD Medical GmbH, Berlin, Germany, has been used in the Department of Ophthalmology, Dietrich-Bonhoeffer-Klinikum, Neubrandenburg following cataract surgery.

Months or years after this surgery, opacification of the posterior lens capsule with corresponding visual impairment may occur. With the help of a Nd:YAG laser, this so-called secondary cataract, can usually be eliminated quickly and painlessly.

2. SYNOPSIS

2.1 Aim of the study

This study protocol is designed to collect surgical and postoperative information to determine the PCO rate and PCO dynamics of the MICS L-313 intraocular lens. Depending on the result, these findings may influence the further development of the intraocular lens L-313.

2.2 Population

- Up to 3000 patient's eyes should be recruited
- Patients after cataract surgery with implantation of MICS-IOL L-313

2.1.1 Inclusion criteria for the patients

- Willingness to give written consent
- Patients after cataract surgery with implantation of the MICS IOL L-313
- Age of 18 years or older

2.1.2 Exclusion criteria for the patients

- Patients having their residence outside the area of our referring ophthalmologists of Neubrandenburg
- Patients who die within the observation period

2.3 Study-design

- retro-/prospective, monocentral study

2.4 Study-investigation-plan

- intraoperative und postoperative data gathering from the medical records
- Filing a questionnaire to the patients, asking for diagnosis and treatment of PCO (if necessary, a postoperative examination in the Department of Ophthalmology Neubrandenburg in order to determine the PCO, if no PCO was documented or if not known)

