2.5 Safety-related results

- Occurrence of intraoperative and postoperative adverse events

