4.4 Documentation

The data is collected via the Excel program (Version 14.0.7166.5000/32-Bit, Microsoft, USA). The intraoperative information is taken from the surgical books and the respective surgical reports. The following data is recorded.

- Operation Date
- Name and address of the patient
- Date of birth
- Which eye (right/left)
- Anesthesia
- Power of the MICS-IOL
- Surgeon
- Intraoperative parameters (Phaco time, Phaco machine, Hardness of the lens, etc.)
- Intraoperative special features/complications

The postoperative documentation is taken from the charts or the questionnaire filled in by the patient. Here, the patient should indicate (if possible with a date) whether a Nd:YAG laser treatment has already been performed on the operated eye. If a patient does not provide clear information due to ignorance, then the respective registered ophthalmologist will be contacted.

In patients without a previously diagnosed or treated PCO (in the hospital or at the ophthalmologist), the information date is documented instead of the laser date. If necessary, the patient will be brought to the hospital once in order to assess the present capsule opacity.

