4.5 Postoperative Examination

Only if the planned number of 388 eyes is not reached by sending a questionnaire to the patients, the patients, who could not provide information because of uncertainty, are brought to the Eye Hospital Neubrandenburg for the assessment of the postoperative PCO. In this case, a proband study insurance and a travel insurance will subsequently be paid.

As part of the study, the following investigations are then carried out:

- a) General and ophthalmological patient's history
 - Questionnaire on general and ophthalmological medication
 - General pre-existing conditions
 - Previous operations
- b) Best corrected visual acuity
 - ETDRS Panel / Snellen Panel: Letters on panels with decreasing size from top to bottom to determine the visual acuity
- c) Slit lamp examination
 - Eye examination with the help of a microscope to observe the eye under high magnification to assess the anterior, middle and posterior structures of the eye
- d) Assessment of posterior capsule (possibly with dilated pupil)

The newly obtained findings are then supplemented in the data collection table.

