7.1 Adverse events

An adverse event (AE) is an adverse medical event, accidental illness or injury, or adverse clinical sign in a study subject during the observation period, with or without association with the MICS L-313 intraocular lens.

All study eye AEs must be recorded in the data collection table. Each AE must be classified according to the degree of damage to the patient, as well as with respect to the IOL or its implantation procedure.

AEs are classified as follows:

- MILD: Complaints without interruption of the daily routine
- MODERATE: Complaints that reduce or affect daily routines
- SEVERE: Disability with inability to work or to cope with normal daily routine

Changes in a chronic condition or illness are not considered to be AEs.

Cataract surgery-related AEs to be expected are listed here:

- Anterior capsular tear
- Posterior capsular rupture
- Vitreous humor in the anterior chamber
- Intraoperativ hyphema
- Loss of vitreous humor
- Choroid bleeding, effusion or detachment
- Iris injury or trauma
- Corneal damage
- Zonular dialysis
- Fibrin reaction
- Persistent Hyphema
- Corneal clouding, corneal edema
- Retinal complications
- eye movement disorders

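### Postoperative adverse events are a stated safety result, but no described data source asks all participants or their ophthalmologists about events other than PCO

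*Combined protocol and SAP*

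**What the plan says.** The safety result in section 2.5 is "Occurrence of intraoperative and postoperative adverse events". Section 7.1 defines an AE over the observation period, whether or not it is related to the lens, and adds that "All study eye AEs must be recorded in the data collection table". Under section 3 the observation period of each patient runs until PCO is diagnosed or ruled out.

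The postoperative data sources are described as follows:

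- **Records.** Section 2.4 plans "intraoperative und postoperative data gathering from the medical records".
- **Charts or questionnaire.** Section 4.4 states: "The postoperative documentation is taken from the charts or the questionnaire filled in by the patient".
- **Questionnaire content.** Section 2.4 describes it as "Filing a questionnaire to the patients, asking for diagnosis and treatment of PCO". Section 4.4 says the patient should indicate "whether a Nd:YAG laser treatment has already been performed on the operated eye", with a date if possible.
- **Outside ophthalmologist.** Section 4.4: "If a patient does not provide clear information due to ignorance, then the respective registered ophthalmologist will be contacted".
- **Hospital examination.** Section 4.5 provides a history, visual acuity, slit lamp and capsule assessment, but "Only if the planned number of 388 eyes is not reached by sending a questionnaire to the patients", and then only for patients who were uncertain.

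Section 5 plans a Kaplan-Meier analysis with the PCO rate as its main question. Neither section 5 nor section 7.1 gives an AE analysis, an AE denominator or a category for unknown AE status.

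**The concern.** The safety result covers all postoperative events in the study eye, while the described collection is built around PCO. A patient who answers the laser question clearly is, as far as the plan describes, asked nothing else about the eye, and the ophthalmologist is not contacted.

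The plan expects relevant care outside the hospital: it refers to referring, treating and registered ophthalmologists as places where patients are seen or as sources of information (exclusion criteria, sections 3 and 4.4). Section 4.2 says that 80% of eligible patients had their surgery 3 to 5 years ago. The plan sends a questionnaire about PCO instead of relying on charts alone. The same reasoning applies to other late events, for which no comparable enquiry is described.

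At stake is what the safety result can support. Missing events push a frequency in one direction only, towards making the lens look safer, and nothing in the data would show a reader how many were missed.

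**Working it through.** This is a question of data sources, so the main check traces each source against the requirement in section 7.1.

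| Source | Reaches all participants? | Described as covering events other than PCO? |
|---|---|---|
| Records or charts (2.4, 4.4) | Yes, for what has been filed; nothing says outside records are obtained | Yes, for what has been filed |
| Questionnaire (2.4, 4.4) | Sent to all | No: PCO and Nd:YAG only |
| Outside ophthalmologist (4.4) | No: unclear answers only | No: follows directly on the laser question |
| Hospital examination (4.5) | No: only if 388 eyes are not reached, and only uncertain patients | Yes, through history and slit lamp |

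No row combines active enquiry, all participants and events other than PCO. Intraoperative events are a separate matter: section 4.4 takes them from the surgical books and reports, so this gap does not touch them.

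**The plan's own figure.** The only number needed is the planned size. With the section 4.2 inputs (SD 0.492, difference 0.1):

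16 × 0.492² / 0.1² = 16 × 0.242064 / 0.01 = 387.30, rounded up to 388.

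The 388 is reproduced. (Section 4.2 prints 387.88 before rounding, which changes nothing.) Section 4.2 calls these patients and section 4.5 calls them eyes; eyes are used below.

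**Direction and illustrative size.** If a share *m* of true events is missed:

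recorded rate = true rate × (1 − *m*).

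The documents give neither the true rate nor *m*. The values below are assumptions, chosen only to show the range, with 388 eyes:

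| Assumed true rate | True events | Recorded if *m* = 50% | Recorded if *m* = 75% |
|---|---|---|---|
| 1% | 3.9 | 1.9 (0.5%) | 1.0 (0.25%) |
| 2% | 7.8 | 3.9 (1.0%) | 1.9 (0.5%) |
| 5% | 19.4 | 9.7 (2.5%) | 4.9 (1.25%) |

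For example, 388 × 0.05 = 19.4 and 19.4 × (1 − 0.50) = 9.7. If nothing is missed (*m* = 0) there is no bias. The table shows the direction and how the result scales; it does not estimate the bias in this study.

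**The case against.** Several counter-arguments have force.

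- **The form is not in the supplied text.** Section 2.4 is a synopsis bullet, and section 4.4 does not claim to list every item. A reader might infer that the form has no AE question; the documents do not establish that. The point concerns the questionnaire as described, and the fix is conditional on what the form contains.
- **No rule codes a missing AE as no event.** A reader might infer that outside events are counted as absent. The plan states no such rule and no AE rate. What stands is narrower: such events go unrecorded, and with no category for unknown status they cannot be separated from no event.
- **The hospital chart is not the only possible source.** The plan speaks of medical records and charts without limiting them to the hospital, outside letters may be filed there, and the section 4.5 examination would pick up some events. These routes are partial, and none is a systematic enquiry.
- **The share of care given outside is unknown.** The plan shows that outside ophthalmologists are involved but not what share of complications they manage. The size of the bias therefore cannot be stated.
- **The AE window is not the time since surgery.** It closes when PCO is diagnosed or ruled out, so 3 to 5 years since surgery overstates the window for eyes with earlier PCO. This limits the events that count and has to be respected in the fix.
- **Recall is imperfect.** A free-text answer years later, from patients averaging 74.73 years at operation, will not give a complete AE record. That is a reason for caution in reporting, but it does not remove the mismatch.

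None of these arguments supplies a source that asks every participant, or every ophthalmologist, about other events.

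**Conclusion.** The point holds as a mismatch between the safety result in sections 2.5 and 7.1 and the sources described in sections 2.4, 4.4 and 4.5. Followed as written, the plan under-ascertains postoperative events that are managed outside and not filed in the charts, and any postoperative AE frequency would be biased low.

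This rests on two assumptions: that the form contains no more than the plan describes, and that at least some events are managed elsewhere without reaching the records. The documents provide no basis for estimating the amount, and the halving or quartering shown above should not be read as a finding.

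The PCO analysis, the sample size and the intraoperative AEs are unaffected. It should be corrected because it changes what the safety result can conclude and the remedy is cheap.

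**What to change.** **If the forms can still be changed.** Check whether the form already asks about other events. If it does, say so in sections 2.4 and 4.4. If not, add one open item, for example: *Since the surgery, have you had any other problem, treatment or operation on the operated eye? If yes, what and when?* Use the dates to count only events within the plan's own observation period, that is, up to PCO diagnosis or exclusion. The item belongs on the form sent to everyone, because a line added only to the ophthalmologist query would reach only patients with unclear answers. The cost is a slightly longer form, a small notification to the ethics committee if one is needed, and answers limited by recall.

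**If the forms have already gone out.** Restate section 2.5 as intraoperative AEs plus postoperative AEs documented in the available records, and in the section 4.5 examination where it was done. Bring the recording requirement in section 7.1 into line with that source, and report no postoperative AE rate for the full observation period. This needs no new data; the cost is a narrower safety claim.

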2.5 Safety-related results

- Occurrence of intraoperative and postoperative adverse events

3. DURATION OF THE STUDY

The patients participating in the study had undergone cataract surgery at the Department of Ophthalmology in Neubrandenburg. Thus, the date of the operation is known.

The duration of the observation is dependent on the duration of the postoperative period to the diagnosis of the PCO or until the exclusion of the PCO due to the information provided by the patient or by the treating ophthalmologist for each individual patient. The observation period and thus also the study period therefore varies with each patient.

The period for data collection started with the first implantation of the intraocular lens L313 in September 2008 and is scheduled to end in December 2016.

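### The adverse-event window closes at PCO diagnosis, so later events in those eyes, including complications of Nd:YAG treatment, fall outside the AE and SAE definitions

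*Combined protocol and SAP*

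**What the plan says.** - **Safety result.** Section 2.5 names it as "Occurrence of intraoperative and postoperative adverse events". It gives no time limit.
- **AE definition.** Section 7.1 covers an "adverse clinical sign in a study subject during the observation period, with or without association with the MICS L-313 intraocular lens". The same section adds that "All study eye AEs must be recorded in the data collection table". Its list of expected events includes retinal complications.
- **Length of observation.** Section 3 says: "The duration of the observation is dependent on the duration of the postoperative period to the diagnosis of the PCO". Where there is no PCO, observation ends when the patient or the ophthalmologist supplies the information that rules it out. The section then concludes: "The observation period and thus also the study period therefore varies with each patient".
- **Calendar period.** Section 3 separately gives a data-collection period from September 2008 to December 2016.
- **Dates recorded.** Section 4.4 records the laser date or, for an eye with no PCO diagnosed or treated, the date of the information.
- **SAEs.** Section 7.2 defines these as AEs that meet further criteria and requires them to be reported to the sponsor within one week.
- **PCO treatment.** Section 1 says: "With the help of a Nd:YAG laser, this so-called secondary cataract, can usually be eliminated quickly and painlessly".

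**The concern.** Ending follow-up at PCO diagnosis is right for a time-to-PCO analysis. Section 7.1 borrows the same period for safety, so the length of AE follow-up depends on the outcome under study. It ends early in the eyes that develop PCO, which are also the eyes that may go on to a further procedure.

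Section 2.1 says the findings may influence further development of the lens, so the safety result has a use. A reader of that result would expect intraoperative and postoperative events for every study eye. Under the definitions they would get events up to PCO diagnosis in some eyes and up to the last information date in the others, with nothing in the report to show the difference.

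**Working it through.** The point rests on reading the sections together. The documents give no figure for it.

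**Step 1: which period governs AEs?** Section 7.1 refers to the observation period, and only section 3 gives that period a length. The calendar span to December 2016 cannot be what is meant. Section 3 calls that span the period for data collection, and says the observation period differs from patient to patient, which a fixed calendar window does not.

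**Step 2: apply it to two eyes.** Suppose both are operated on the same day and both patients reply at year 4 (timings invented for illustration).

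| Eye | Window ends (section 3) | Retinal complication in year 3 |
|---|---|---|
| PCO diagnosed at month 18 | month 18 | not an AE |
| No PCO | year 4 (information date) | AE |

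The first eye's laser treatment follows its diagnosis, so any complication of that treatment is also outside. If the laser date in section 4.4 were taken as the end instead, everything after the laser would still be outside. An eye whose PCO is first found at its last contact loses nothing.

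**Step 3: does another section widen the window?**
- Section 2.5 sets no window, so the 7.1 definition applies to it.
- The 7.1 rule that all study-eye AEs be recorded uses a term already limited by the definition above it.
- Section 7.2 defines SAEs as a kind of AE and inherits the limit, including for the report to the sponsor.
- No section sets safety follow-up after PCO diagnosis or after laser treatment.

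**Step 4: rough scale, on assumptions.** The planned number in section 4.2 reproduces: 16 × 0.492² / 0.1² = 387.30, rounded up to 388. The printed 387.88 fits an unrounded SD of about 0.4924.

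The documents give no PCO rate for L-313, so a range of cumulative proportions p is assumed. If 0.492 is the SD of a yes/no outcome (also an assumption), p(1 − p) = 0.492² = 0.2421, which gives p = 0.411 or 0.589. The number of eyes whose window closes at PCO is 388 × p. With a constant PCO hazard and a common cut-off, the share of eye-time after PCO is 1 − p / (−ln(1 − p)).

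| Assumed p | Eyes of 388 | Share of eye-time outside the AE window |
|---|---|---|
| 0.10 | 39 | 5% |
| 0.20 | 78 | 10% |
| 0.30 | 116 | 16% |
| 0.411 | 159 | 22% |
| 0.589 | 229 | 34% |

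These are shares of observation time. They do not translate into numbers of AEs.

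**The case against.** The strongest reply is that section 3 describes variable follow-up for PCO and never says that AE recording stops. Section 2.4 asks about treatment as well as diagnosis, section 4.4 records the laser date, and sections 2.5 and 7.1 speak broadly of postoperative and of all study-eye AEs. A wider intent is plausible, and later events may be noted from charts in practice. That much stands. Still, none of these sections redefines the period on which the AE definition depends. If a wider window was meant, the sections conflict and need reconciling.

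Four stronger conclusions that a reader might draw are not supported.

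- **Intraoperative events are left out.** Section 3 does speak of a postoperative period, but sections 2.4, 2.5, 4.4 and 7.1 all provide for intraoperative events. They are plainly meant to be covered.
- **A fifth to a third of AEs would be lost.** The proportions rest on an assumed binomial SD, taken in section 4.2 from publications on other lenses, and on assumed timing. Many of the events listed in 7.1 belong to the operation itself, before any PCO. The documents give no rate of post-laser or late events, and the sentence in section 1 shows only that laser treatment is used.
- **AE rates would be biased between eyes with and without PCO.** The plan contains no AE rate per unit time and no AE comparison by PCO status. The unequal windows affect what is counted, not a planned test.
- **The main result is affected.** Stopping at PCO is appropriate for the Kaplan-Meier analysis in section 5.

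One practical objection also stands: rewording 7.1 does not by itself capture the events. Section 2.4 mentions no AE question in the questionnaire, and under section 4.4 the ophthalmologist is contacted only when the patient's information is unclear.

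**Conclusion.** The point holds as an inconsistency between the safety result and the definitions that deliver it. Taken as written, sections 3 and 7.1 leave study-eye events after PCO diagnosis outside the AE and SAE definitions, while PCO-free eyes are covered to the information date. That is narrower than section 2.5 promises.

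The conclusion depends only on the wording and not on any PCO rate. Its size in missed AEs is unknown, and the eye-time figures above are illustrations under stated assumptions. The primary PCO estimate does not change. This is a worthwhile, inexpensive correction to the safety part of the plan.

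**What to change.** - In 7.1, give AEs their own window, independent of PCO status: from the start of cataract surgery to the last information date for that eye, whether that is a questionnaire, ophthalmologist's information, a chart entry or an examination.
- Give this window its own name, because the exclusion criteria in 2.1.2 also use the term observation period. Keep the section 3 rule for the Kaplan-Meier PCO analysis only.
- Reconcile sections 2.5, 3, 4.4 and 7.1 with the new window. Section 7.2 then follows, since SAEs are defined as AEs.
- Tabulate AEs after Nd:YAG treatment separately.

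**Cost.** The edit is short, with one more table row. The real cost is some extra chart abstraction after the PCO or laser date. Not every record is at hand: an eye lasered outside the hospital whose patient gives a clear answer triggers no contact with the ophthalmologist. Where no outside record is obtained, report post-laser AEs for that eye as not ascertained, not as absent, and state how many eyes this concerns.

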4. IMPLEMENTATION

4.1 Screening

The selection of patients is carried out by the documentation books kept in the operating rooms of the Department of Ophthalmology and the respective surgical reports. Once a patient meets the inclusion criteria, the patient is contacted and asked to participate in the study.

4.2 Patients recruitment

For statistical evaluation, the number of cases is determined using the following formula * before patient recruitment.

$$n = 16 \times \frac{\delta^2}{d^2}$$

n=Subjects number
δ=Standard deviation
d= relevant difference

$$n = 16 \times \frac{0,492^{2**}}{0,1^2} = 387,88 \approx 388 \text{ Patients}$$

80% of the patients eligible for the study underwent surgery 3 to 5 years ago. At a follow-up period of 3 to 4 years, the response rate is 13.9% ***.

This results in:

$$n = \frac{388}{0,139} = 2.791,37 \approx 2.792 \text{ Patients}$$

Due to the relatively high average age (at the time of the operation) of 74.73 years, an even lower response rate is to be expected. For this reason, up to 3000 patients will be contacted.

The patient receives the patient's study information sheet, the declaration of consent as well as an informative sheet for the patients regarding PCO. While retaining one copy of these documents, the patient is required to return the other copy and the completed data collection form to the eye clinic. Only when the signed declaration of consent is present, the patient participates in the study.

*Kutschmann M et al. Aspekte der Fallzahlkalkulation und Powerberechnung anhand von Beispielen aus der rehabilitationswissenschaftlichen Forschung. Rehabilitation 2006;45:377-384

** Zur Vergleichsbasis sind 2 Publikationen mit dem Thema der nachstarquote herangezogen worden:

1. Peterman K, Wildgrube M „A-Konstante und Nachstarquote der Intraokularlinse Akreos™ AO MI-60“, Oktober 2009,
2. Spyridaki M, Höh H „Vergleich von 4 MICS-Intraokularlinsen (ThinLens, AcriSmart, CareFlex, und Acriflex) im Hinblick auf ihre Neodym:YAG-Laser-Kapsulotomieraten“ April 2009

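### The difference-based rationale for 388 does not match the planned one-group Kaplan-Meier rate, and both 388 and 3,000 are counted in patients in one section and in eyes in another

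*Combined protocol and SAP*

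**What the plan says.** **Sample size.** Section 4.2 states "For statistical evaluation, the number of cases is determined using the following formula * before patient recruitment". The formula is n = 16 × SD²/d², with SD 0.492, d = 0.1 and the legend "d= relevant difference". The result is given as 388 patients. Dividing by an expected response of 13.9% gives 2,792, which is raised: "up to 3000 patients will be contacted". A footnote to the SD says "Zur Vergleichsbasis sind 2 Publikationen mit dem Thema der nachstarquote herangezogen worden", that is, two publications on PCO rates served as a basis for comparison. No rate from either is given.

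**Analysis.** All patients have the L-313 lens (2.2 and the inclusion criteria). Section 5 makes determining the PCO rate the main question and names Kaplan-Meier as the only method. Section 3 lets observation time differ between patients. Alpha, power, comparator and test are not stated.

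**Unit.** Section 2.2 says "Up to 3000 patient's eyes should be recruited". Section 4.5 says "Only if the planned number of 388 eyes is not reached by sending a questionnaire to the patients", in which case "the patients, who could not provide information because of uncertainty, are brought to the Eye Hospital Neubrandenburg", and adds "In this case, a proband study insurance and a travel insurance will subsequently be paid". Section 4.3 leaves open whether the identification code belongs to a patient or to an eye. No section says how two eyes of one patient are analysed.

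**The concern.** A sample size justified by a difference should belong to a plan that compares something. Here nothing is compared, so a reader cannot tell from 4.2 what 388 is meant to secure.

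The unit matters in two places. Two eyes of one patient are not independent, so 388 eyes can carry less information than the 388 patients derived in 4.2, and an interval that treats eyes as independent would then be too narrow. In addition, 4.5 uses the count to decide on a recall visit that brings insurance costs. With the unit switched between sections, the same returns could trigger recall under one section and not under the other.

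**Working it through.** **1. The plan's own figures.** 16 × 0.492²/0.1² = 16 × 0.242064/0.01 = 387.30. The plan prints 387.88, which would need an SD of about 0.4924; both round up to 388. Then 388/0.139 = 2,791.4, rounded up to 2,792. Both stated results reproduce.

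**2. What the formula can mean.**
- Two groups: 2 × (1.960 + 0.842)² = 15.70, close to 16. This is the size per group for two-sided 5% and 80% power; the unrounded constant gives 380 per group. The plan has no second group.
- One group: a 95% interval of total width w has w = 2 × z × SD/√n. With z = 2 and w = 0.1, n = 16 × SD²/0.1² = 387.3, again 388. With z = 1.96, n = 372. This fits the analysis, but the plan does not state it as the target.

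**3. Precision of 388 independent patients.** 1.96 × 0.492/√388 = 0.0490, or ±4.9 points, before allowing for censoring. If 0.492 is the SD of a yes/no outcome (my inference), p(1 − p) = 0.242, so p is about 41% or 59%.

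**4. If 388 means eyes.** Let f be the share of patients who contribute both eyes and ρ the between-eye correlation. The documents give neither. I assume f = 0.4 (range 0.2 to 0.6) and ρ = 0.3 to 0.7, and use a simple-proportion approximation, not a clustered Kaplan-Meier.
- Patients behind 388 eyes = 388/(1 + f): 277 at f = 0.4 (323 at 0.2, 243 at 0.6).
- Design effect = 1 + ρ × 2f/(1 + f). At f = 0.4: 1.17 for ρ = 0.3 and 1.40 for ρ = 0.7.
- Effective n = 388/1.17 = 331, down to 388/1.40 = 277.
- Half-width = 1.96 × 0.492/√331 = 5.3 points, up to 1.96 × 0.492/√277 = 5.8 points.
- A nominal 95% interval that treats these eyes as independent covers about 93% to 90%.

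**5. Recall condition, with 3,000 patients contacted.** The count that matters is of patients or eyes with clear information, not of replies.
- In patients: 388/3,000 = 12.9% of those contacted.
- In eyes: 388/(3,000 × 1.4) = 9.2% (10.8% at f = 0.2, 8.1% at f = 0.6).
- If 10% of answers stay unresolved (assumed), the response needed is 12.93/0.9 = 14.4% in patients and 9.24/0.9 = 10.3% in eyes.
- At exactly 13.9% response there are 417 replies, so in patients recall is triggered once more than 417 − 388 = 29 (7%) are unresolved.

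Between the two thresholds, 4.2 and 4.5 lead to opposite decisions. Section 4.2 itself expects a response below 13.9%.

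**The case against.** **The number changes nothing.** 388 suits a one-group interval, the formula's source is not available here, and the footnote suggests that a historical comparison may have been intended. This stands as far as the number goes, and 388 should stay. A reader might infer that the study is underpowered, because 388 split over two groups would give 51.7% power. The documents do not support that: there is no second group and no test. A one-sample test of a 0.1 difference would need only 190.

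**Clustering is assumed.** This stands. The loss of independent units arises only if some patients contribute both eyes. The documents give no share, and the questionnaire described in 4.4 refers to a single operated eye. The plan also specifies no interval, so the coverage figures describe what would follow if eyes were treated as independent.

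**The unit alone does not decide who is examined.** This also stands. Sections 2.4 and 4.4 allow a hospital examination where needed, without the 388 condition, and 4.4 contacts the ophthalmologist first. A reader might also take 12.9% and 9.2% as response rates; they are shares with clear information.

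**No time point is named.** A reader might infer that precision must fall sharply by year 5. In a simulation with 388 independent patients, exponential event times, 41% PCO at 3 years and follow-up assumed to be 80% at 3–5 years, 10% at 0.5–3 and 10% at 5–8, the Kaplan-Meier half-widths are 5.0, 5.4 and 6.9 points at 3, 4 and 5 years. But the 80% figure in 4.2 is time since surgery, and collection runs to December 2016. With follow-up one year longer they are 4.9, 5.1 and 5.3; with two years, 4.9, 5.0 and 5.0. The fall is therefore not established, and Kaplan-Meier also serves the stated interest in PCO dynamics.

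**3,000 as a limit on contacts in eyes.** A reader might infer from 2.2 that fewer patients are contacted than 4.2 requires. Section 2.2 speaks of recruitment, while 4.2 states the contact number in patients, so that reading is strained.

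**Conclusion.** The point holds on the text: the rationale in 4.2 refers to a difference that the plan does not test, and 388 and 3,000 each carry two units. Confidence is high for the conflicting units and the missing comparator only.

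The consequences are minor to moderate and conditional. 388 is not shown to be too small. The loss of precision from counting eyes is about 0.4 to 0.9 points of half-width under the assumed 40% with both eyes and correlation 0.3 to 0.7; it is zero if every patient contributes one eye. The conflict over recall is practical because the plan's own expected response lies near or inside the range where the two counts disagree, but its size depends on the same unstated share and on how many answers stay unresolved.

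**What to change.** Keep 388, 2,792 and 3,000.

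1. **Section 4.2.** Replace the difference rationale with a precision: 388 independent patients give a 95% interval of about ±5 points for a rate near 41% or 59%, before allowing for censoring. Add that this covers sampling error only, not bias from non-response, expected at 86.1% (100 − 13.9) or more. If a comparison with the footnoted publications is intended, state the reference rate, its time point and the test.
2. **Sections 2.2, 4.2 and 4.5.** Count patients for both numbers, as the calculation in 4.2 does, and say in 2.2 that 3,000 is the number contacted. In section 5, either analyse one eye per patient by a rule fixed in advance, or include both eyes with a patient-clustered variance.
3. **Sections 2.4, 4.4 and 4.5.** Reconcile the condition for recall in 4.5 with the unconditional option of an examination in the other two.

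Optional, in section 5: name in advance a time that most patients reach, and report the Kaplan-Meier rate there with its 95% interval and numbers at risk, alongside the full curve.

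**Cost.** The text changes are one paragraph in 4.2, two or three sentences in 5, and a line in each of the other sections. The real downside is that counting patients makes recall, with its insurance cost, more likely, so it should be budgeted. Recall reaches only patients who were uncertain and cannot make up for non-response. If 388 is still missed, report the interval reached: by 1.96 × 0.492/√n, 300 patients give ±5.6 points and 240 give ±6.2.
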